8.2 Derived Variables

The following sections provide a general description of the derived variables for data analyses. Separate analysis dataset specifications provide full details on all data derivations and transformations.

8.2.1 Reference Dates

There are two reference dates defined in this study:

- The efficacy reference date is the date of randomization and will be used to calculate study day as well as time to event for efficacy measures
- The safety reference date is the treatment start date, and will be used to calculate study day for safety measures.

8.2.2 Study Day for Safety Measures

If the date of interest occurs on or after the safety reference date then the safety study day will be calculated as (date of interest - safety reference date) + 1. If the date of interest occurs before the safety reference date then the safety study day will be calculated as (date of interest – safety reference date). There is no safety study day 0.

8.2.3 Study Day for Efficacy

If the date of interest occurs on or after the efficacy reference date then efficacy study day will be calculated as (date of interest - efficacy reference date) + 1. If the date of interest occurs prior to the efficacy reference date then efficacy study day will be calculated as (date of interest – efficacy reference date). There is no efficacy study day 0.

8.2.4 Durations

Durations of events (eg, duration of an AE or medication) calculated in days will use only dates based on the algorithm given below:

- (End date – Start date) + 1

Durations calculated in hours (h), such as duration of infusion, will be calculated using date/time variables shown below:

- (End date/time – Start date/time)

Where durations calculated in days have to be reported in months or years, the following approach will be taken:

$$\text{Months} = \text{days} / 30.4375$$

$$\text{Years} = \text{days} / 365.25$$

8.2.5 Baseline Definition

Baseline is defined as the most recent, non-missing value prior to the date of first infusion of study treatment. For subjects who do not receive study treatment during the study, baseline is defined as the latest, non-missing collected value on or before Visit 2. Subjects without such a result will be considered as missing the baseline value.

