- K:** Local laboratory values obtained as part of standard of care testing for the index acute myocardial infarction event and before obtaining written informed consent should be used to determine study entry and eligibility for infusion 1. However, if results (for ALT, total bilirubin and / or serum creatinine) are not available, then a blood sample must be obtained for the local laboratory testing.
- L:** **For subjects who received infusion 1 of investigational product  $> 12$  hours and  $< 48$  hours after IV contrast administration:** local laboratory serum creatinine value must be obtained before the infusion for comparison with the local laboratory baseline value and reviewed by the investigator. A blood sample for local laboratory testing to assess dosing eligibility for infusion 2 should not occur earlier than 72 hours following the infusion 1.
- M:** During study conduct, the Independent Data Monitoring Committee (IDMC) may make a recommendation to permit discontinuation of blood sampling at Visit 3 and Visit 4 for local laboratory and / or central laboratory biochemistry testing. If the IDMC so recommends, study investigators will be notified by the Executive Committee chairperson that these routine laboratory assessments are no longer required and eligibility for all subsequent infusions is to be based on clinical assessment (ie, starting with infusion 2 / Visit 3).
- N:** Blood sample is to be taken before the start of infusion. This blood sample must be sent to the central laboratory for study analysis purposes.
- O:** Blood samples are to be collected from all subjects at baseline and Visit 6 (Day 29). Immunogenicity testing will be performed using samples from approximately the first 600 subjects (approximately 300 CSL112 and 300 placebo) and oversight will be provided by the IDMC ([Section 8.1.3.6](#)).
- P:** Blood samples are to be collected from all subjects at baseline and Visit 6 (Day 29). Nucleic acid testing and serology (parvovirus B19) will be performed using samples from approximately 300 randomly selected subjects (approximately 150 CSL112 and 150 placebo).
- Q:** Future biomedical research testing includes samples collected at baseline that are intended for storage and / or future analyses (eg, pharmacogenomics).

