### 8.5.1 Visit 1 (Screening)

All subjects must provide written informed consent before any study-specific assessments or procedures are performed. Written informed consent is not required for assessments or procedures performed according to standard of care (eg, for diagnosis or treatment); results from such assessments may be used in the determination of study eligibility.

Subjects will be assessed for eligibility at screening (Visit 1). Screening / eligibility assessment should occur before or on the day of hospital discharge. Before infusion 1 of investigational product is administered, the subject must be clinically stable and meet all of the inclusion and none of the exclusion criteria ([Section 4.1](#)). Hepatic and renal eligibility must be confirmed by the investigator and there must be no suspicion of AKI ([Section 4.2.1](#)).

Subjects who complete all of these assessments and who fulfill all eligibility criteria (ie, eligible subjects) will be enrolled into the study. If the subject is not eligible for the study, the subject information and primary reason for screen failure must be entered in the IRT.

Screening and randomization of subjects may occur on the same day (Day 1 of the Active Treatment Period) provided that the minimum time window after FMC for the index event is met. All tests and procedures that are required to be performed to determine subject eligibility (ie, screening and randomization) must be performed with enough time to administer the investigational product within this timeframe. If angiography is planned for treatment of the index MI, randomization must occur after the procedure has been performed and stability of serum creatinine confirmed at least 12 hours after IV contrast administration.

The following procedures will be conducted and documented at the Screening Visit:

- Informed consent.
  - All subjects must provide written informed consent before any study-specific assessments or procedures are performed. Written informed consent is not required for assessments or procedures performed according to standard of care (eg, for

diagnosis or treatment); results from such assessments may be used in the determination of study eligibility.

- Informed consent for FBR (optional).
- Medical and surgical history.
- Prior / concomitant medication review.
- Review of inclusion and exclusion criteria.
- IRT subject registration and randomization (if eligible).

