  - If the subject is not eligible for the study, the primary reason for screen failure must be entered in the IRT system.
- Pregnancy test (if applicable).
- Demography (year of birth, years of age, sex, race, and ethnicity).
- Height.
- Vital signs.
- Directed physical examination.
- Body weight.
- Blood sample for local laboratory testing (ALT, total bilirubin, and serum creatinine to confirm infusion eligibility), unless already collected as part of standard of care.
- AE / SAE monitoring.
- EQ-5D-3L questionnaire.

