## **8.5.2 Active Treatment Period**

### **8.5.2.1 Visit 2 (Infusion 1)**

Infusion 1 must be administered in the timeframe as detailed in [Section 4.2.1](#).

Before infusion 1 of investigational product, hepatic and renal eligibility based on test results from the local laboratory must be confirmed by the investigator, and there must be no suspicion of AKI ([Sections 4.2.1](#) and [8.5.1](#)).

Before the start of infusion, perform the following assessments:

- Prior / concomitant medication review.
- Vital signs.
- Blood sample for central laboratory testing (biochemistry panel and hematology).

- Blood sample for immunogenicity testing (to be retained in the case of a subject experiencing serious hypersensitivity or suspected angioedema during infusion of investigational product infusion).
- Blood sample for parvovirus testing.
- Blood sample for FBR (if subject consented).
- Blood sample for PK / PD assessment (at selected sites).
- AE / SAE monitoring.

Administer the first IV infusion of investigational product (placebo or CSL112) ([Section 6.2](#)).

At the end of the infusion, perform the following assessments:

- AE / SAE monitoring.
- MACE endpoint assessment.
- Blood sample for PK / PD assessment (at selected sites)

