**Apolipoprotein A-I**

---

Central laboratory data for ALT and serum creatinine will be evaluated to assess the non-inferiority of CSL112 relative to placebo when approximately 20% of subjects have completed Visit 6 (Day 29).

Hepatic evaluation will be based on unconfirmed elevations in ALT ( $> 3 \times \text{ULN}$ ) at any time up to Day 29. The treatment difference in the incidence rates along with 2-sided 95% confidence interval for the treatment difference will be estimated. If the upper limit of the confidence interval is lower than the pre-specified non-inferiority margin of 3%, the hepatic effect of CSL112 will be considered to be non-inferior to placebo. In addition to evaluation of the non-inferiority analysis, the IDMC will review AEs that may be related to hepatic dysfunction (ie, right upper quadrant pain, anorexia, generalized pruritus, jaundice, and encephalopathy). The IDMC, using their clinical judgment and the outcome of non-inferiority evaluation, may recommend that central laboratory samples prior to infusions 2 and 3 be discontinued in the remaining subjects.

Renal evaluation will be based on the percentage of subjects with a change from baseline (before infusion 1) in serum creatinine  $\geq 0.3 \text{ mg/dL}$  ( $27 \mu\text{mol/L}$ ) at any time up to Day 29. The treatment difference in the incidence rates along with a 2-sided 95% confidence interval for the treatment difference will be estimated. If the upper limit of the confidence interval is lower than the pre-specified non-inferiority margin of 5%, the renal impact of CSL112 will be considered to be non-inferior to placebo. The IDMC has the discretion to recommend that laboratory samples in remaining subjects be discontinued.

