Evaluation of hepatic function will be based on a demonstration of non-inferiority of CSL112 to placebo in the incidence rate of elevations in ALT ($>3 \times \text{ULN}$) at any time up to Day 29. The placebo event rate of 2.7% is taken from the Phase 2b study AEGIS-I. A non-inferiority margin similar in magnitude to the background event rate is considered to be a clinically meaningful criterion and thus, the margin is set at 3%. The treatment difference in the incidence rates will be estimated along with a two-sided 95% CI using the Newcombe-Wilson method [[Newcombe, 1998](#)]. If the upper limit of the CI is less than the pre-specified non-inferiority margin of 3%, the effect of CSL112 on the liver will be considered to be non-inferior to placebo. In addition to the evaluation of the non-inferiority analysis, the IDMC will review AEs that may be related to hepatic dysfunction (right upper quadrant pain, anorexia, generalized pruritus, jaundice, and encephalopathy). The IDMC, using their clinical judgment and the outcome of non-inferiority evaluation, may recommend discontinuation of central laboratory sampling before infusions 2 and 3 in the remaining subjects.

The renal function assessment will be based on acute kidney injury (AKI), defined as a change from baseline (pre-infusion 1) in serum creatinine $\geq 0.3 \text{ mg/dL}$. The background rate of AKI is derived as a weighted average of the observed placebo event rate (3.9%) from AEGIS-I in subjects with normal renal function or mild renal impairment (RI) and the renal event rate [[Tsai, 2014](#)] for subjects with moderate RI (~10%) and either STEMI or NSTEMI. Assuming that 75% of randomized subjects in the current study will have normal renal function or mild RI, and 25% will have moderate RI, the background event is estimated to be 5.4% [$0.75*3.9 + 0.25*10$]. A non-inferiority margin similar to the background rate is considered to be a clinically meaningful criterion for the comparison of CSL112 to placebo. The treatment difference in the incidence rates along with a two-sided 95% CI [[Newcombe, 1998](#)] will be estimated. The upper limit of the CI will be compared to the pre-defined non-inferiority margin of 5%. The renal impact of CSL112 will be considered to be non-inferior to placebo if the upper limit of the CI is less than 5%. The IDMC has the discretion to

recommend discontinuation of laboratory samples prior to infusions 2 and 3 in remaining subjects.

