8.2.6 Change from Baseline

Change from baseline will only be calculated for measures that have post-baseline records.

Change from baseline is calculated as:

$$(\text{Visit value}) - \text{Baseline value}.$$

Percentage change from baseline is calculated as:

$$((\text{change from baseline}) / \text{baseline value}) * 100$$

If either the baseline or visit value is missing, the change from baseline and percentage change from baseline is set to missing as well.

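### SAP 8.2.5 cuts baseline off at the date of the first infusion, which read literally discards the Visit 2 pre-infusion central sample; the cut-off should be the start of that infusion.

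*SAP*

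**What the plan says.** For treated subjects, SAP 8.2.5 reads: "Baseline is defined as the most recent, non-missing value prior to the date of first infusion of study treatment". For subjects never dosed, the same section lets the Visit 2 value count. A subject with no qualifying value has a missing baseline. SAP 8.2.6 adds: "If either the baseline or visit value is missing, the change from baseline and percentage change from baseline is set to missing as well".

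SAP 11.6.1 bases laboratory analysis on central results, apart from ALT and bilirubin for potential hepatic injury, and says the 8.2.5 baseline governs change from baseline. SAP 11.2.2 defines the acute kidney injury (AKI) event of special interest from central creatinine.

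The protocol fixes when samples are drawn:
- Screening (8.5.1) lists "Blood sample for local laboratory testing (ALT, total bilirubin, and serum creatinine to confirm infusion eligibility", with no central sample.
- Visit 2 (8.5.2.1) lists "Blood sample for central laboratory testing (biochemistry panel and hematology" among the assessments made before infusion 1. Note N to the Schedule of Assessments says: "Blood sample is to be taken before the start of infusion".
- Screening need not fall on an earlier day: "Screening and randomization of subjects may occur on the same day (Day 1 of the Active Treatment Period".

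Elsewhere the baseline is tied to the infusion and not to its date. The interim renal review uses "change from baseline (pre-infusion 1) in serum creatinine" in SAP 4.6.1.2, and Protocol 10.3.6.2 says: "Renal evaluation will be based on the percentage of subjects with a change from baseline (before infusion 1) in serum creatinine".

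**The concern.** A rule that stops at the date of the first infusion excludes anything collected on that date, including samples taken before the infusion began. The scheduled central baseline sample is one of these. The text applied as written would leave treated subjects, who are the only members of the Safety Analysis Set, without a central-laboratory baseline unless a central sample happened to be drawn on an earlier day.

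The outputs at stake are:
- the AKI event of special interest;
- the creatinine change categories and multiples of baseline, and the creatinine-rise summary by ACE inhibitor or ARB use;
- central-laboratory change and shift tables;
- baseline lipids and the low/normal HDL subgroup.

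Vital-sign change would be measured from the older screening reading. The final AKI analysis and the IDMC renal review share the 0.3 mg/dL (27 µmol/L) threshold but, read literally, would rest on different baseline rules. Renal safety is a question the protocol itself raises in Section 1.4.

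**Working it through.** The plan gives no figure to reproduce here. The check applies the SAP's own date rules to the protocol's sampling schedule.

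**1. Can the date be read as date and time?** The SAP's usage is against it. Section 8.2.4 separates day-based durations, which use dates alone, from hour-based durations, which use date/time variables. Section 8.3.1 refers to the start of the first infusion, or to the time before the first dose, where the moment matters. Section 8.3.2 expressly includes the infusion date for baseline medications, and 8.2.5 expressly includes Visit 2 for untreated subjects.

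**2. Where does the Visit 2 sample fall?** Let d be the date of infusion 1. SAP 8.2.2 gives safety study day = (date of interest − d) + 1 for dates on or after d. A Visit 2 sample dated d has study day (d − d) + 1 = 1. The literal 8.2.5 rule needs a date earlier than d, which is study day −1 or lower because there is no day 0. The sample fails.

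**3. Scheduled central samples** (Schedule of Assessments; Protocol 8.5):

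| Panel | Dated before d | On d, pre-infusion | After dosing |
|---|---|---|---|
| Biochemistry | 0 | 1 (Visit 2) | 3 (Visits 3, 4, 6) |
| Hematology | 0 | 1 (Visit 2) | 1 (Visit 6) |

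Accepted as baseline under the literal rule: 0 of 1 for each panel. Accepted under a rule that stops at the start of infusion: 1 of 1.

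**4. Consequence for change.** By 8.2.6, a missing baseline makes every change missing. That covers all 3 scheduled post-dose central creatinine values, or the 1 remaining at Visit 6 if the IDMC drops sampling at Visits 3 and 4 under note M.

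**5. Vital signs.** There are 2 scheduled readings before infusion 1, at Visits 1 and 2. The literal rule rejects Visit 2, so at most 2 − 1 = 1 remains, and 0 if screening was also on Day 1.

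**6. Exception.** Protocol 4.2.1 and 8.1.3.2.1 allow one draw to serve both local and central testing. A subject whose combined draw predates d keeps a central baseline. The documents give no count of such subjects.

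**7. Left out of the scope.** eGFR is excluded because SAP 8.2.9 derives it from local values as well. PK and PD are excluded because SAP Sections 12 and 13 do not invoke 8.2.5. The primary efficacy model has no laboratory covariate.

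**The case against.** The strongest reply is that this is loose wording with an obvious meaning. SAP 8.2 describes its subsections as general and leaves full derivations to separate dataset specifications, which may already flag the Visit 2 sample correctly. Several passages treat that sample as baseline: the interim renal review in both documents, the parvovirus analysis in SAP 11.7.4, and the central-laboratory comparison in Protocol 4.2.2.2. The literal outcome would empty the central change tables, and the dry runs foreseen in SAP 4.4 would expose it before database lock. The reference to pre-infusion in SAP 4.6.1.2 can be read as explaining what baseline means, not as setting a competing rule. The contrast with the medication wording in 8.3.2 is weak, because medications are handled separately. The counts above are of scheduled samples, not of affected subjects.

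Much of this stands. The intent is clear, the error would probably be caught, and the number of subjects is unknown. What does not follow is that the text needs no change. An unseen specification does not amend the SAP, and passages that show a different intent conflict with 8.2.5 without overriding it. SAP Section 7 requires departures from the SAP to be identified in the study report, so a silent correction would itself be a deviation. A programmer trying to obey the rule might substitute a local screening creatinine and mix laboratories.

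**Conclusion.** The rule is wrong as written and should be corrected. Per treated subject, it accepts 0 of 1 scheduled pre-dose central samples and leaves all 3 scheduled post-dose central creatinine changes undefined (1 if note M is applied). For vital signs it accepts at most 1 of 2 pre-dose readings.

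This rests on two assumptions: that the Visit 2 sample carries the same date as infusion 1, as the schedule provides, and that no central sample was drawn on an earlier day. The likely practical harm is small, because the intended meaning is recoverable from other sections. The defect nevertheless sits in the definition that governs the safety change-from-baseline analyses, including AKI. No primary or key secondary efficacy result, alpha level or sample size depends on it.

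**What to change.** Reword 8.2.5 so that, for treated subjects, baseline is the last non-missing value collected before the start date and time of the first infusion. Add that a sample recorded under nominal Visit 2 as pre-infusion counts as baseline if its collection time is missing. State that analyses of central-laboratory data take their baseline from the central laboratory. SAP 11.6.1 largely implies this, but saying it rules out a local substitute.

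The cost is one or two sentences in the SAP and a matching check of the dataset specification. The Visit 2 samples are already scheduled, so no new data are needed. The change brings 8.2.5 into line with the interim renal review and the sampling schedule.

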8.2.6 Change from Baseline

Change from baseline will only be calculated for measures that have post-baseline records.

Change from baseline is calculated as:

$$(\text{Visit value}) - \text{Baseline value}.$$

Percentage change from baseline is calculated as:

$$((\text{change from baseline}) / \text{baseline value}) * 100$$

If either the baseline or visit value is missing, the change from baseline and percentage change from baseline is set to missing as well.

8.2.7 Multiple Assessments

All data will be reported to according to the nominal visit date for which it was reported (that is, no visit windows will be applied during dataset creation). All other unscheduled data will be included in worst case post-baseline summaries.

Data from all assessments (scheduled and unscheduled), including multiple assessments, will be included in listings.

8.2.8 Actual Treatment

The subjects' actual treatment will be derived from exposure data. Kit ID dispensed by the IRT and actual kit ID used will be recorded. If a subject's actual treatment is the same as the assigned treatment, then actual treatment is the assigned treatment. If a subject receives a study treatment that is different from the assigned treatment, then the following rule will apply: the actual treatment group will be set to CSL112 if at least one infusion of CSL112 is administered regardless of randomized treatment; if a subject assigned to CSL112 receives only infusions of placebo then the actual treatment will be defined as placebo.

8.2.9 Derivation Algorithms

Derivation of BMI

BMI will be calculated using the following formula:

$$\text{BMI (kg/m}^2\text{)} = \text{Weight (kg)} / [\text{Height (m)}]^2$$

The height and weight measured at Screening will be used (if available).

Derivation of Hospitalizations for coronary, cerebral, or peripheral ischemia:

- Total number of hospitalizations per subject will be derived by defining a cumulative count variable that is incremented with each new date of positively-adjudicated hospitalization. The analysis dataset will include one record per subject, with a count variable containing the total number of hospitalizations.

Derivation of Indirect bilirubin:

The calculation of indirect bilirubin is applicable when both TBili and direct bilirubin are reported by the central laboratory.

- Indirect bilirubin ($\mu\text{mol/L}$) = TBili ($\mu\text{mol/L}$) – direct bilirubin ($\mu\text{mol/L}$)

Derivation of Estimated Glomerular Filtration Rate (eGFR):

For the purpose of safety analyses, the eGFR value will be calculated for both local and central laboratory reported results. The CKD-EPI equations shown in [Table 8-1](#) will be used:

Table 8-1 **CKD-EPI Equations**

Race and Sex	Serum Creatinine (mg/dL (μ mol/L))	Equation
Black		
Female	≤ 0.7 (≤ 62)	$eGFR = 166 * (Scr/0.7)^{-0.329} * 0.993^{age}$
	> 0.7 (> 62)	$eGFR = 166 * (Scr/0.7)^{-1.209} * 0.993^{age}$
Male	≤ 0.9 (≤ 80)	$eGFR = 163 * (Scr/0.9)^{-0.411} * 0.993^{age}$
	> 0.9 (> 80)	$eGFR = 163 * (Scr/0.9)^{-1.209} * 0.993^{age}$
White or Other		
Female	≤ 0.7 (≤ 62)	$eGFR = 144 * (Scr/0.7)^{-0.329} * 0.993^{age}$
	> 0.7 (> 62)	$eGFR = 144 * (Scr/0.7)^{-1.209} * 0.993^{age}$
Male	≤ 0.9 (≤ 80)	$eGFR = 141 * (Scr/0.9)^{-0.411} * 0.993^{age}$
	> 0.9 (> 80)	$eGFR = 141 * (Scr/0.9)^{-1.209} * 0.993^{age}$

The CKD-EPI equation can be expressed in a single equation as:

- $eGFR \text{ (derived)} = 141 * \min(Scr/\kappa, 1)^\alpha * \max(Scr/\kappa, 1)^{-1.209} * 0.993^{age} * 1.018 \text{ [if female]}$
 $\text{ x } 1.159 \text{ [if black]}$

Where Scr is serum creatinine, κ is 0.7 for females and 0.9 for males, α is -0.329 for females and -0.411 for males, min indicates the minimum of Scr/κ or 1, and max indicates the maximum of Scr/κ or 1. In Table 8-1, the multiplication factors for race and sex are incorporated into the intercept, which results in the different intercepts for race and sex combinations.

Stratification and Prognostic Factors

The stratification variables, demographic characteristics, baseline risk factors and/or prognostic variables, and variables indicating compliance with evidence-based therapy will be added to the dataset at a minimum to describe the study population, and to support analyses of efficacy data and subgroups: The code descriptions will be used as the labels for each subgroup level. When performing analyses using stratification factors, the original data used for randomization will serve as the primary source. A sensitivity analysis may be performed if there is a substantial difference between the strata used for randomization and corrected strata. Distinct naming conventions will be used such that identification of the source of stratification factors will be straightforward.

The variables defined below include the study treatment to which subjects are randomized as well as the factors used for stratifying the randomization. These variables will be included in the ADaM datasets to support analysis. In addition, some of the variables listed will be included in the subgroup analysis of the primary endpoint. For such variables, the group coded as 0 will serve as the reference group for statistical comparisons. In other words, if the estimated hazard ratio is less than 1 it will be interpreted as favoring the non-reference group relative to the reference group.

Randomization Variables:

Treatment:

1 = CSL112

0 = Placebo

Index MI Type:

1 = STEMI

0 = NSTEMI

Management of Index MI:

1 = Managed with PCI

0 = Managed medically

Region (1):

1 = North America

2 = Latin America

3 = Western Europe

4 = Central and Eastern Europe

0 = Asia Pacific

Demographic Characteristics:

Gender:

1 = Female

0 = Male

Age at baseline categorized as follows:

1 = Less than 65 years old

0 = Greater than or equal to 65 years old

Race categorized as:

- 3 = Other/multiracial (includes Native American, Pacific Islander, Multiracial, & other)
- 2 = Asian
- 1 = Black/African-American
- 0 = White

Ethnicity categorized as:

- 1 = Hispanic
- 0 = Non-Hispanic

Region (2):

- 1 = North America (U.S. and Canada)
- 0 = Rest of World (RoW)

Baseline Risk Factors

Meet modified enrichment criteria (diabetes on pharmacotherapy or at least two of age ≥ 65 years, PAD, history of prior MI (excluding index MI):

- 1 = Yes
- 0 = No

Planned Staged PCI:

- 1 = Yes
- 0 = No

Diabetes Mellitus on Pharmacotherapy:

- 1 = Yes
- 0 = No

Prior Myocardial Infarction (MI) [excluding index MI]:

- 1 = Yes
- 0 = No

Prior PCI [excluding index MI]:

- 1 = Yes
- 0 = No

Peripheral Artery Disease:

1 = Yes

0 = No

Renal Function (based on calculated eGFR measurement as given in [Table 8-1](#))

0 = Normal renal function: ≥ 90 mL/min/1.73 m²

1 = Mild renal impairment: $\geq 60 - <90$ mL/min/1.73 m²

2 = Moderate renal impairment: $\geq 30 - <60$ mL/min/1.73 m²

HDL (mg/dL):

1 = Low: <1.04 μ mol/L/40 mg/dL for men and <1.3 μ mol/L/50 mg/dL for women

0 = Normal: ≥ 1.04 μ mol/L/40 mg/dL for men and ≥ 1.3 μ mol/L/50 mg/dL for women

Medication usage at the time of Index MI:

Thrombolytic use:

1 = Yes

0 = No

Medication usage at the time of randomization:

Aspirin use:

1 = Yes

0 = No

PCSK9 Inhibitor use:

1 = Yes

0 = No

P2Y12 Anti-platelets use:

1 = Yes

0 = No

Dual anti-platelet therapy (aspirin and P2Y12)

1 = Yes

0 = No

Statin use:

0 = None

1 = High Intensity

2 = Moderate Intensity

3 = Low Intensity

Beta-blockers

1 = Yes

0 = No

Non-statin lipid modifying agents (including niacin and fibrates):

1 = Yes

0 = No

Angiotensin Converting Enzyme Inhibitors (ACEI) or Angiotensin II Receptor Blockers (ARB):

1 = Yes

0 = No

SGLT2 Inhibitor:

1 = Yes

0 = No

